#### 15.2.2.3 Relationship to Study Drug

The causal relationship of the study drug to an AE will be rated according to the following 4-point scale:

- **Unrelated:** Clearly and incontrovertibly due only to extraneous causes, and does not meet criteria listed under possible or probable
- **Unlikely:** Does not follow a reasonable temporal sequence from administration; may have been produced by the participant’s clinical state or by environmental factors or other therapies administered
- **Possible:** Follows a reasonable temporal sequence from administration; may have been produced by the participant’s clinical state or by environmental factors or other therapies administered

- **Probable:** Clear temporal association with improvement on cessation of study drug or reduction in dose. Reappears upon re-challenge or follows a known pattern of response to the study drug

#### 15.2.2.4 Action Taken

The action taken toward the study drug in response to an AE will be listed as one of the following:

- **None:** no change in study drug dosage was made
- **Reduced:** dose of study drug was reduced
- **Discontinued** the study drug was permanently stopped

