#### **FOR INDIVIDUAL PARTICIPANTS:**

Participants who develop a severe adverse event or laboratory abnormality will not receive any additional doses and will be monitored until resolution of the AE or the return of laboratory abnormality to the acceptable screening value(s). Study drug may be re-initiated after consultation with medical monitor and sponsor. Any participant with:

- elevated ALT or AST greater than 5 X ULN should have dosing with study drug stopped and have laboratory tests repeated every 3-4 days until levels return to less than or equal to 1.5 X ULN. If the medical monitor and investigator are in agreement, study drug may be continued while a confirmatory ALT/AST is obtained within 3 days. If the confirmatory ALT/AST tests are below 5 X ULN, study drug may be continued. The frequency of the laboratory tests may be modified after discussion with the medical monitor if the liver enzymes are in a decreasing trend.
- Elevated ALT or AST greater than 3 X ULN in combination with total bilirubin > 2 X ULN or INR > 1.5 X ULN OR an ALT or AST > 3 X ULN with the appearance of fatigue, nausea, vomiting, right upper quadrant pain or tenderness, fever, rash, and/or eosinophilia (>5%) should have dosing with study drug stopped and have laboratory testing repeated every 3-4 days. If the medical monitor and investigator are in agreement, study drug may be continued while a confirmatory laboratory testing is obtained within 3 days. If these criteria are no longer met, study drug can be continued at the discretion of the medical monitor and investigator. The frequency of the laboratory tests may be modified after discussion with the medical monitor if the laboratory tests are trending towards normal.
- An increase in serum creatinine by 0.3 mg/dL (24.4 micromol/L) or 150% of baseline that is without clinical explanation of another etiology will result in repeated serum chemistry testing within 3-7 days. If the serum creatinine elevation is confirmed on repeated testing the study drug will be discontinued. If the serum creatinine elevation resolves upon

subsequent testing after study drug is discontinued the study drug may be restarted with serum creatinine monitoring at the discretion of the medical monitor and investigator.

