- An increase in serum calcium to  $\geq 10.5$  mg/dL (2.63 mmol/L) that is without clinical explanation of another etiology will result in repeated serum chemistry testing within 3-7 days. If the serum calcium elevation is confirmed on repeated testing the study drug will be discontinued. If the serum calcium elevation resolves upon subsequent testing after study drug is discontinued the study drug may be restarted with serum calcium monitoring at the discretion of the medical monitor and investigator.
- Note: Fractional excretion of calcium will be monitored in each participant and interpreted in conjunction with serum creatinine and serum calcium. Given the ability of fractional excretion to fluctuate, no upper limit for discontinuing study drug based on fractional excretion of calcium has been set but it may be used as a stopping rule if persistent unexplained increases in fractional excretion of calcium are observed.

**Note:** Any unanticipated SAEs that are ‘related’ should be reported to the National Institute on Aging within 48 hours of knowledge of the same.

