#### **9.4 *Withdrawal of Participants***

A participant should be withdrawn from the study if any of the following occur:

- 1) Withdrawal of participant consent.
- 2) Investigator determines that withdrawal from the study is in the best interest of the participant.
- 3) Major protocol violation (i.e., circumstances where confounding conditions make it impossible to derive sound scientific or medical conclusions from the primary endpoint data generated on a participant).
- 4) Any condition, injury, or disease that becomes apparent during the study and necessitates the termination of the participant from the study; including events detailed in Section 7.3.1 - Safety Stopping Rules.
- 5) Administrative reason (e.g., termination of the clinical study by a Regulatory Agency or the Sponsor).

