### **Laboratory Abnormality**

A laboratory abnormality is any clinically significant laboratory abnormality suggesting a disease or organ toxicity and which is of a severity requiring active management (i.e., changes of dose, discontinuation of drug, more frequent follow-up, medical treatment or a diagnostic investigation). Laboratory abnormalities are also considered AEs, if clinically significant.

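### A temporary stop of study drug has no action-taken code, and adverse events that stop drug without study withdrawal are not summarised by arm

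*Protocol*

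**What the plan says.** **Stopping and restarting.** In Protocol 7.3.1, the lead-in for individual participants says: "Participants who develop a severe adverse event or laboratory abnormality will not receive any additional doses". It then adds: "Study drug may be re-initiated after consultation with medical monitor and sponsor". The creatinine rule says: "If the serum creatinine elevation is confirmed on repeated testing the study drug will be discontinued". If the value then resolves, "the study drug may be restarted with serum creatinine monitoring at the discretion of the medical monitor and investigator". The calcium rule has the same structure and ends: "the study drug may be restarted with serum calcium monitoring at the discretion of the medical monitor and investigator". The synopsis repeats these rules. Section 7.3.1 also provides for dosing to be suspended in all participants while safety data are reviewed, after which it may resume.

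**Recording.** Protocol 15.2.2.4 gives three codes for the action taken with study drug: None (dosage unchanged), Reduced, and Discontinued, meaning that "the study drug was permanently stopped".

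**Reporting.** SAP 8.2 plans summaries of adverse events by system organ class and preferred term, severity and relationship, and of serious events and events that led to study withdrawal. Appendix 2 lists the matching tables under 14.3.1 and 14.3.2; the one on withdrawal is Table 14.3.2.2.

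**Withdrawal.** Protocol 9.4(4) calls for withdrawal for a condition that "necessitates the termination of the participant from the study; including events detailed in Section 7.3.1 - Safety Stopping Rules". Section 9.5.1 names drug discontinuation and study withdrawal as separate occurrences when it asks for the date and reason on the CRF.

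**The concern.** The primary objective is safety and tolerability. Whether an event made a participant pause or stop the drug is one of the plainest measures of tolerability. The protocol foresees pauses, then provides no way to record one correctly as the action taken for the event. The same sequence matters for causality: under 15.2.2.3 a Probable rating draws on improvement after the drug is stopped and on recurrence when it is given again.

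The SAP adds a second gap. Someone who pauses or permanently stops drug because of an adverse event, but stays in the study, appears in no table that links the event to the stop. In arms of 7, a few such cases could change the impression of how a dose is tolerated.

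**Working it through.** The plan states no figure on this point, so the check sets the texts side by side and counts.

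**1. Does any code fit a stop followed by a restart?**

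| Code in 15.2.2.4 | Meaning | Fits? |
|---|---|---|
| None | Dosage unchanged | No: doses were withheld |
| Reduced | Lower dose given | No: dosing stopped, and restart is not tied to a lower dose |
| Discontinued | Permanent stop | No: drug was restarted |

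Result: 0 of 3. The lead-in, the creatinine rule and the calcium rule of 7.3.1 each permit a restart, so each can produce an event that cannot be coded correctly. A study-wide suspension that is later lifted does the same for the participants whose events triggered it.

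**2. Does any planned adverse event table cover drug stops?** Tables 14.3.1.1 to 14.3.1.5 make 5, and Tables 14.3.2.1 to 14.3.2.3 make 3; 5 + 3 = 8. By title they cover: overall summary, MedDRA term, intensity, relationship, at least moderate and related, serious events, study withdrawal, and deaths. Result: 0 of 8 cover interruption or discontinuation of study drug in participants who remain in the study.

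**3. What do the other outputs show?** Listing 16.2.5.1 gives drug administration, and Table 14.1.3 gives treatment and total dose. Table 14.3.4.8 gives individual laboratory profiles where a result was clinically significant. Listing 16.2.7.1 reproduces the adverse event CRF data, so it would carry whatever code was entered. A reader could reconstruct a pause from these, participant by participant. None of them summarises by arm which events led to it.

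**4. What would be lost if a drug stop were treated as study withdrawal?** Take a stop after Day 43 in the primary study.

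- Post-baseline cognitive visits (SAP 9.1) are Days 43, 85, 127 and 169, so 3 remain. The early-discontinuation visit (Protocol 10.2.12) includes cognitive testing and supplies 1. Net loss: 3 − 1 = 2.
- Post-baseline UCB-J scans (Protocol 10.2.8 and 10.2.12) are Days 85 and 169, so 2 remain. The early-discontinuation visit includes a scan and supplies 1. Net loss: 2 − 1 = 1.

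This counts assessments only; the one supplied may fall well before Day 169.

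**5. Weight of one participant.** 1/7 = 14.3% of an arm (Protocol 17.2).

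**The case against.** The best defence is that little information is lost. Section 9.5.1 puts the date and reason for stopping drug on the CRF. SAP 5.1 sends all CRF data to listings. A comments listing (16.2.2.2) and narratives of other significant events are planned, and with 7 per arm every case can be read individually. The CRF itself is not among the documents and may offer more options than 15.2.2.4 does. A table could also be added when the report is written. This stands against any claim that interruptions would be invisible. It does not supply a correct code, and a by-arm summary assembled later from listings is a weaker basis for a primary tolerability statement than one planned in advance.

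Three stronger readings are tempting, and the documents do not support them.

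- *That 9.4(4) turns every stop under 7.3.1 into study withdrawal.* The clause is limited to conditions that necessitate termination. A stop that 7.3.1 allows to be reversed does not obviously do so, and 9.5.1 separates the two. The wording could be clearer, no more. The harms are also alternatives: if a stop is handled as withdrawal, its event enters Table 14.3.2.2; if it is not, no visits are lost. Replacement in the same arm (7.5) and tracking of unresolved events for up to 30 days (15.2.3) soften the first case further.
- *That 7.3.1 contradicts itself on who approves a restart.* The lead-in requires consultation with the medical monitor and sponsor. The creatinine and calcium rules give discretion to the medical monitor and investigator. Both can be followed.
- *That 7.3.1 conflicts on dosing during the 3-7 day creatinine or calcium retest.* The specific rules stop drug only on confirmation, so the natural reading is that dosing continues until then. A conflict arises only if "severe" in the lead-in does not qualify the laboratory abnormality and the broad definition in 15.2.1 is brought in. The liver rules do address dosing pending a retest, so a sentence here would help, but it is a clarification.

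**Conclusion.** The point holds for recording and reporting. The protocol permits temporary stops, and 0 of 3 action-taken codes describes one, so following the text produces a wrong entry. None of the 8 planned adverse event tables captures event-driven drug stops in participants who stay in the study, although tolerability is part of the primary objective. Dosing, exposure and laboratory outputs show such stops only indirectly.

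The conclusion assumes that the CRF follows 15.2.2.4 and that at least one temporary stop occurs; the documents give no expected number. No power or error-rate figure is affected. A reader might infer that a stop after Day 43 would cost 3 cognitive visits and both scans. Even if it were handled as withdrawal, the net loss in the primary study is 2 cognitive visits and 1 UCB-J scan. This is a defect that should be corrected, not one that threatens the trial's validity.

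**What to change.** 1. Protocol 15.2.2.4: add an Interrupted code, with stop and restart dates, and carry it to the CRF.
2. SAP 8.2 and Appendix 2: beside Table 14.3.2.2, add a table by arm of adverse events that led to interruption and, separately, to permanent discontinuation of study drug.
3. Protocol 9.4(4): add one sentence saying that stopping drug under 7.3.1 is not by itself study withdrawal and that scheduled assessments continue.

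Optional clarifications in 7.3.1 and its synopsis copy: say whether drug is held while a creatinine or calcium retest is pending, and who makes the final decision on restart.

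The cost is one CRF option with two dates, one SAP table and a short protocol amendment. No visit or test is added beyond those already scheduled.

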#### 15.2.2.5 Outcome of Adverse Event

The outcome of an AE will be recorded as one of the following:

- **Recovered:** fully recovered or the condition has returned to the level observed at baseline
- **Recovered with sequelae:** resulted in persistent or significant disability or incapacity; the nature of the sequelae should be specified
- **Not yet recovered**
- **Death**

### 15.2.3 Adverse Event Follow-up

Adverse events requiring therapy must be treated with recognized standards of medical care to protect the health and well-being of the participant.

Any participant who has any AE (whether serious or non-serious) or clinically significant (in the Investigator's opinion) abnormal laboratory test values will be evaluated by the Investigator or a monitoring physician, and will be treated and followed up until the symptoms or values return to normal or acceptable levels, as judged by the Investigator and the Sponsor.

Adverse events that are unresolved at end of study or upon early withdrawal will be tracked at least weekly by site staff until resolution, for 30 days, or until the participant is lost to follow-up

(defined as failure to respond to three phone messages left on separate days and one certified letter requesting follow-up).

Participants will be instructed to inform site staff of any AEs occurring during the 30-day period after discharge or early withdrawal.

Any follow-up information available at the time of the participant's end of study will be included in the clinical study report.

Any SAE that is considered to be unexpected and related to the study drug occurring after the end of study should be forwarded to the Sponsor. These cases will be handled and submitted as expedited reports, but will not be included in the clinical study report.

### ***15.3 Serious and Other Significant Adverse Events***

#### **15.3.1 Definition of a Serious Adverse Event**

A serious adverse event is any untoward medical occurrence that

- **Results in death.** Death is not an event per se but rather an outcome. Note that any event resulting in a fatal outcome must be fully documented and reported, including deaths that occur within 30 days after treatment ends and irrespective of the causal relationship to the study drug.
- **Is life-threatening.** Life-threatening refers to an AE in which the participant was at immediate risk of death at the time of the event. It does not refer to an event, which may have caused death, if it was more severe.
- **Requires in-patient hospitalization or prolongation of existing hospitalization.** Hospitalization means that the participant was admitted to hospital or that existing hospitalization was extended as a result of an event. Hospitalization describes a period of at least 24 hours. Over-night stays for observation; stays at the emergency room or treatment on an outpatient basis do not constitute a hospitalization. However, medical judgment must always be exercised and, when in doubt, the case should be considered serious (i.e. if the case fulfills the criterion for a medically important event). Hospitalization for administrative or social purposes does not constitute an SAE. Hospital admissions and/or surgical operations planned before study inclusion are not considered AEs if the illness or disease existed before the participant were enrolled in the study, provided that the condition did not deteriorate during the study.

- **Results in persistent or significant disability/incapacity.** Disability/incapacity means a substantial disruption of a person's ability to conduct normal life functions. If in doubt, the decision should be left to medical judgment by the Investigator.
- **Is a congenital anomaly/birth defect.** Any congenital anomaly or birth defect observed in any offspring of the participant conceived during treatment with the study drug.
- **Is an important medical event.** Important medical events are events that may not be immediately life-threatening or result in death or hospitalization but may jeopardize the participant or may require intervention to prevent one of the other outcomes listed in the definition above. Examples of important medical events include AEs that suggest a significant hazard, contraindication or precaution, occurrence of malignancy or development of drug dependency or drug abuse. Medical and scientific judgment should be exercised in deciding whether events qualify as medically important.

An AE caused by an overdose or medical error is considered serious if a criterion listed in the definitions above is fulfilled.

The following are not considered SAEs:

- A pre-existing condition that is present prior to or at the start of the study that did not worsen
- Hospitalizations for treatment which were elective or preplanned, for a pre-existing condition unrelated to the indication under study that did not worsen
- Admission to a hospital or other institution for general care, not associated with any deterioration in condition.

### **15.3.2 Serious Adverse Event Reporting by the Investigator to the Sponsor**

Any SAE that occurs after a participant has entered the study, whether or not related to study drug, must be reported to the Sponsor or the Sponsor's agent immediately (within 24 hours) via telephone or facsimile. If initially reported via telephone, this must be followed-up by a facsimile of the written SAE report. The Investigator must report all SAEs occurring from the time the participant signs the ICF until 30 days after last treatment with the study drug.

A completed Serious Adverse Event Report Form with the best possible details must be transmitted to the Sponsor representative by facsimile within 24 hours of knowledge of the SAE according to contact details as specified below:

**Sponsor Representative and Contact Information for SAE Reporting:**

**15.3.3 Handling of Follow-up Information**

Follow-up information may be required or additional information may be received by the Sponsor (e.g., evolution of the SAE, other signs or symptoms, final diagnosis, final outcome, hospital discharge summary, or autopsy report). The same procedures and timelines as for initial reporting, listed above, should be followed for any follow-up information. If necessary, the study site will be visited to collect additional information.

Follow-up information is required on all SAEs until one of the following criteria is satisfied:

- The final outcome of the case is known
- The event is resolved or the medical condition of the participant is stabilized
- No further information is available
- Sponsor assessment has been finalized

**15.3.4 Reporting and Follow-up of Pregnancy**

When an Investigator becomes aware of the pregnancy of a female participant, the Investigator must withdraw the participant from the study and follow the pregnancy until termination or until the child is 1 month old. The pregnancy will be reported immediately by telephone and by faxing a completed Pregnancy Report to the Sponsor within 24 hours of knowledge of the event. The pregnancy will not be processed as an SAE; however, the Investigator should notify the Sponsor or the Sponsor's agent of the outcome of the pregnancy by submitting a follow-up Pregnancy Report. Additionally, if the outcome of the pregnancy meets the criteria for immediate

classification of an SAE (e.g., spontaneous or therapeutic abortion, stillbirth, neonatal death, or congenital anomaly), the Investigator will report the event by phone and by faxing a completed SAE Report Form to the Sponsor within 24 hours of knowledge of the event.

### **15.3.5 Expedited Reporting of Serious Adverse Events**

#### ***15.3.5.1 Responsibilities***

The Sponsor is responsible for ensuring the timely reporting of SAEs to Regulatory Authorities and all Investigators who participate in the clinical development program of the study drug. It is the responsibility of the Investigator to provide the Sponsor with the case information such that reporting timeline demands of applicable Regulatory Authorities can be met.

#### ***15.3.5.2 Expedited Reporting***

All AEs that are serious, unexpected, and considered related to the study drug judged by either Sponsor or the Investigator require expedited reporting. All available information relevant to the evaluation of the SAE will be reported. Serious adverse events will be considered reportable regardless of whether or not the study drug was used in accordance with the provisions in the protocol.

Adverse events which are serious, but expected, or those which are not associated with the study drug will only be participated to expedite reporting if they are required to be reported to an authority according to national requirements.

#### ***15.3.5.3 Timelines***

Fatal or life-threatening serious unexpected related cases require rapid reporting. Regulatory Authorities shall be notified as soon as possible but no later than 7 calendar days after first knowledge by the Sponsor representative, followed by as complete a report as possible within 8 additional calendar days.

Serious unexpected related cases that are not fatal or life-threatening must be submitted as soon as possible, but no later than 15 calendar days after first knowledge by the Sponsor representative that the case meets the minimum criteria for expedited reporting.

It is the responsibility of the Investigator to support Sponsor activities needed to meet the aforementioned timelines for Regulatory Authority reporting in the event of an SAE.

